16.0 Potential Benefits to Subjects or Others

There may be no direct and immediate benefit to the participants from this research study. Participants in the study may accrue the benefit of improved mobility, strength and balance and along with the benefits of the yoga and behavioral activation, more motivation to be physically active which could improve symptoms of chronic pain and/or fatigue. The benefit to others is that if this program is proven effective, other low-income older adults, might benefit as well from its future implementation.

18.0 Drugs or Devices

This study does not involve the use or storage of any drug product. All investigational supplies and materials are readily commercially available and are not industry regulated. All study supplies (tablets) will be inventoried and stored in a locked cabinet, behind a locked door by the researchers. Study supplies will be dispensed individually to each participants after enrollment and group assignment.

A&D Medical Premium Wireless Blood Pressure Monitor is an FDA approved, Bluetooth blood pressure cuff that will be utilized to collect participants blood pressure and pulse and transmit the data to the "Activate for Life" application.

The "Activate for Life" app is an application that will be available on participants tablets. This app has the ability to receive Bluetooth data from the A&D wireless blood pressure monitor. The app will also allow participants to enter their pain and fatigue levels on a "1-10" scale, ask participants to input their PA and their use of pain medication for the day, and record thoughts on a voice recorded daily diary. This information will transmit from the application to a firewall protected server at MUSC where it will be available to the research team. No medical information will be stored on the app.

References:

2. Laubenstein, S., & Beissner, K. (2016). Exercise and Movement-based Therapies in Geriatric Pain Management. *Clinical Geriatric Medicine*, 32, 737–762. <http://dx.doi.org/10.1016/j.cger.2016.06.002>
3. Liu, C.J. & Latham, N.K. (2009). Progressive resistance strength training for improving physical function in older adults. *Cochrane Database Systematic Review*, 8(3), CD002759. doi:10.1002/14651858.CD002759.pub2.

Official title: Activate For Life: mHealth Intervention To Address Pain And Fatigue In Lowincome Older Adults Aging In Place

NCT03853148

Document date: 03/12/2021

Analysis plan

Data were analyzed using IBM SPSS Version 26.0. Mean substitution was conducted to account for missing data (these did not represent more than 40% of overall dead data). Repeated measures analysis of variance (ANOVA) was used to determine significant differences for outcome variables between the 3 intervention Arms. Differences were considered statistically significant for *p*-values <0.05. Analyses were similar for outcomes in the caregiver group.

Measures of feasibility including recruitment and reach, fidelity and adherence, formal satisfaction, and drop-out proportions were evaluated. Then 95% confidence intervals for proportions were used to estimate dichotomous outcomes (e.g., the proportion of subjects who: agree to participate out of the number that are approached, the proportion who complete the intervention, the proportion who report satisfaction with the intervention, and the proportion who exit the study prematurely [drop out]). Further, the participants' reasons for drop out, and problems/issues encountered with the intervention were described via frequency distributions. For continuous measures (e.g. satisfaction scores), frequency distributions and the median and mean responses (with 95% confidence intervals) were obtained. Univariate descriptive statistics and frequency distributions were calculated as appropriate for all variables. Demographic variables obtained at baseline were described via measures of central tendency (mean, median), variability and frequency distributions as appropriate. Additionally, characteristics for those who were eligible for study versus those who were not eligible and for those who adhered to the study protocol (study completers) versus those who did not adhere (non-adherers and drop-outs) were compared to better describe the population for this study.

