AIM 1. Integrate evidence-based components of “*Activate for Life*” a telehealth delivered, nurse-led behavioral health program for low income older adults targeting pain and fatigue through balance training (Otago), strengthening and mindfulness (Yoga), and affective state (Behavioral Activation).

We hypothesize that the evidence-based Otago and Yoga components of this intervention will integrate with the ‘infrastructure’ format of the Behavioral Activation mental health treatment insofar as a 60-minute session, 6-10 session intervention will be developed.

Aim 2. Test the feasibility of Activate for Life in terms of its individual components by comparing Otago vs. Otago+Yoga vs. Otago+Yoga+Behavioral Activation in a pilot RCT design with 10 participants in each of the 3 conditions in terms of recruitment, intervention ‘dosage’ (frequency/density), adherence, treatment satisfaction, attrition, rates of missing data, and other feasibility metrics, including qualitative feedback from participants for final intervention refinement.

We hypothesize that adherence will be adequate (65% scheduled activity compliance), satisfaction will be high (above 80%), attrition will be limited (below 25%), and followup data collected (below 20% missing data)

AIM 3. Determine an initial efficacy signal for the intervention that will inform future power estimates.

We hypothesize that the combined intervention will show significant within subject improvement over baseline on measures of pain, fatigue, and depression.

Supplemental ARM 4 - AIM 4. Test the feasibility of a 12-week e/mHealth gentle yoga+yogic breathing (GYYB) intervention for alleviating symptoms of burden in aging Caregivers (CG) of persons (N=20) with dementia (PWD); measure initial changes in stress and QoL indicators in CG and PWD (post- vs. pre-intervention).

Impact. This pilot feasibility study will set the stage for a full scale RCT demonstrating the additive benefit (if present) of each additional component over the CDC approved balance intervention Otago. Self-management of pain and fatigue through strength and balance training in low-income older adults can improve quality of life, decrease health care costs, and increase the ability of the person with these symptoms to age in place.

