3.0 Intervention to be studied

ARMS 1, 2, and 3. Design Overview. Design Overview and Project Timeline:

This 12-week feasibility trial will use a 3x3 repeated measures (treatment x time) between groups randomized trial design to compare Otago (OG) vs. Otago + Yoga (GYB) vs. Otago + GYB + Behavioral Activation (ie., the complete *Activate for Life* intervention) in low-income older adults with chronic pain and/or fatigue at baseline, post-treatment and 3- month follow-up. Participants will be randomly assigned to one of the three conditions. Daily self-monitoring of program component adherence, PROMIS self-report measures of pain, fatigue, anxiety, depression, and social support. Physical activity measures will include actigraphy, steps per day, 2-minute timed walk test, sit-to-stand test, and Mini-Best. Participants will be 30 adults (10 per group) age 60 and above with a PROMIS pain interference score of eight or above and/or a PROMIS pain behavior score of 15 or above (cut points based on a T-score that rescales the raw score into a standardized score with a mean of 50 and a standard deviation (SD) of 10 for each of these instruments).

Alternative design: The progressive nature of this feasibility trial allows the proven evidence-based modalities of OEP and GYB to be combined with behavioral activation to not only address physical activity but also the mental health aspects of chronic pain and fatigue. Therefore, this feasibility trial scaffolds the components to show that the modalities of OEP and GYB are effective and their success is dependent on motivation. However, we are not testing these three interventions alone, or in every possible combination.

Supplemental ARM 4 - Design Overview:

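### The SAP fills missing data by mean substitution and analyses the result as observed. If visit scores were filled, every choice of mean distorts an error rate, an SD or an effect, and the SAP does not say which.

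*SAP*

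**What the plan says.** The SAP's analysis plan reports that "Mean substitution was conducted to account for missing data (these did not represent more than 40% of overall dead data". The next sentence gives the test: "Repeated measures analysis of variance (ANOVA) was used to determine significant differences for outcome variables between the 3 intervention Arms". The significance level is 0.05. For the caregivers it adds: "Analyses were similar for outcomes in the caregiver group". It describes no correction to the error variance or degrees of freedom, no multiple imputation, no likelihood-based model and no sensitivity analysis.

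Protocol section 12.0 (Data analysis plan) has no missing-data rule, so nothing there supplements or overrides the SAP.

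The analysis serves Aim 3 in protocol section 1.0: "Determine an initial efficacy signal for the intervention that will inform future power estimates". Its hypothesis is: "We hypothesize that the combined intervention will show significant within subject improvement over baseline on measures of pain, fatigue, and depression". Aim 2 sets the tolerances for Arms 1-3: "followup data collected (below 20% missing data" and, as a separate metric, "attrition will be limited (below 25" percent. Section 12.0 justifies the 20 caregivers by the wish to determine effect sizes.

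**The concern.** A filled value carries no new information, but ANOVA counts it as a full observation. Depending on the mean used, this understates the error variance, shrinks the spread at follow-up, or pulls the estimated change or arm difference towards zero.

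Three facts needed to tell these apart are missing: the unit filled, the mean used, and the denominator of the 40%. A reader of the Aim 3 or caregiver results therefore cannot tell whether a p-value is too small or an effect is diluted. Both matter in a pilot whose efficacy signal is meant to feed later power estimates.

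**Working it through.** The documents give no SD, effect size or power, so there is no planned figure to reproduce.

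**Inputs from the documents.** Three arms of 10 (Aim 2); 20 caregivers with two visits (section 10.0, Supplemental ARM 4); two visits for most outcomes in Table 2, although section 3.0 plans assessments "at baseline, post-treatment and 3- month follow-up"; 20% missing (Aim 2 limit) and 40% (SAP ceiling, denominator unknown, so an upper case only).

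**Assumptions.** Whole visit scores are filled; normal scores with SD 1 and equal variances; within-person correlation ρ of 0.3, 0.5 or 0.7; missing completely at random at follow-up. Let f be the share observed (0.8 or 0.6).

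**1. Variance used against true variance, same-visit mean.** With n participants, the mean change is the mean of the observed follow-ups minus the mean of all baselines.
- True variance: (1/f + 1 − 2ρ)/n.
- Variance that ANOVA uses: about (f + 1 − 2fρ)/n.
- Ratio: f, for any ρ.

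The time-test error is then about 2(1 − Φ(1.96√f)): 8.0% at f = 0.8 and 12.9% at f = 0.6. For arm-by-time with arm means (2 df), the large-sample version is 0.05^f: 9.1% and 16.6%.

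**2. Follow-up SD.** Filled points add nothing to the sum of squares, so the SD ratio is √[(observed − 1)/(n − 1)].
- Arm mean, 8 or 6 of 10 observed: √(7/9) = 0.88 and √(5/9) = 0.75.
- All-arm mean at the visit, 24 or 18 of 30: √(23/29) = 0.89 and √(17/29) = 0.77.
- Caregivers, 16 or 12 of 20: √(15/19) = 0.89 and √(11/19) = 0.76.

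**3. Dilution of a true 0.50 SD effect.**
- All-arm mean at the visit: an arm difference becomes f × 0.50 = 0.40 and 0.30.
- One mean pooled over visits, with baseline 0 and follow-up −0.50: the fill value is −0.50f/(1 + f) = −0.222 and −0.1875. The change becomes 0.8(−0.50) + 0.2(−0.222) = −0.444, and 0.6(−0.50) + 0.4(−0.1875) = −0.375.
- Own mean with two visits: the fill is the baseline score, so the change becomes 0.40 and 0.30. A correlation of 0.50 becomes 0.8 × 0.50 + 0.2 = 0.60, and 0.6 × 0.50 + 0.4 = 0.70.

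**4. Simulated null error rates** (nominal 5%, at least 20,000 trials per cell; each entry gives 20% then 40% missing).

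| Fill | Time test | Arm-by-time | Combined arm alone (Aim 3) |
|---|---|---|---|
| Arm mean | 7-8%, 12-13% | 8-9%, 14-16% | 7%, 10-12% |
| All-arm mean, same visit | 7-8%, 12% | about 5% | 6%, 7% |
| One mean pooled over visits | 5%, 4% | about 5% | about 5% |
| Own mean | about 5% | 4-5% | 4-5% |

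Caregivers, time test with their visit mean: 7-8% and 12%. With three visits, the time test under arm or same-visit means reaches 10-11% at 20% missing.

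**5. Item-level filling.** For a six-item scale with an assumed inter-item correlation of 0.75, filling from the same person's other items left the error near 5% and changed the SD by 1-3%.

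**The case against.** Several points on the other side are sound.

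- **The harmless case is plausible.** Protocol section 15.0 (Emotional distress) lets participants skip questions, so item gaps are expected. Sections 10.0 and 18.0 also describe daily app entries, another possible unit. If only items were filled, little follows. This stands, and it makes every figure above conditional. It does not excuse leaving the unit unstated.
- **Not every overall mean inflates the time test.** A reader might infer that any overall mean makes it liberal. That holds only for the mean at the same visit. A mean pooled over visits keeps the error at about 4-5%, while shrinking the SD and diluting change.
- **The SAP names the between-arm comparison.** The pooled time test is not the stated test for Arms 1-3. Arm-by-time is inflated only with arm means, and the Aim 3 contrast in the combined arm is at about 6-7% with 20% missing. The time test is, however, the main comparison for the single caregiver group.
- **The share filled is unknown.** A reader might take 40% as the proportion of visits missing, or 25% attrition as the proportion filled. The denominator is unclear, and Aim 2 counts attrition separately from missing data. Neither reading is supported.
- **A mis-sized next trial is not shown.** Nothing says that filled values would be used for planning. As illustration only, a two-group trial needing 63 per arm (0.5 SD, 80% power) would be sized at 63 × 7/9 = 49 or 63 × 5/9 = 35 from arm-mean-filled SDs, but at 99 or 175 from own-mean-diluted effects. The direction depends on the unstated rule.

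**Conclusion.** The SAP applies mean substitution and then ANOVA as if the values were observed, and leaves the rule undefined. If visit scores were filled, all four versions distort something: arm means inflate the tests and shrink the SD; same-visit all-arm means inflate the time test, shrink the SD and dilute arm differences; a pooled mean shrinks the SD and dilutes change; own means dilute change.

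The sizes rest on two visits, 10 per arm, data missing completely at random and an assumed 20% or 40% missing. The actual share and mechanism are not given. If dropout is related to outcome, bias in the means would come on top. A reader might conclude that the reported findings are false positives. The documents do not support that, because item-level filling would leave them nearly intact and two of the four visit-level versions do not inflate error.

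The Aim 2 feasibility proportions are untouched. The point should be fixed, but it does not undermine the pilot's main purpose.

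**What to change.** 1. Do not fill visit-level values. In the software already named, fit a REML linear mixed model to all observed visits with arm, visit and arm-by-visit; unstructured covariance, or compound symmetry if that fails to converge; and Satterthwaite degrees of freedom. Take the combined arm's change from baseline as the Aim 3 contrast. Use visit only for the caregivers.
2. State the missing-at-random assumption.
3. The SAP is written in the past tense, so label the re-analysis as post hoc and show it beside the mean-substituted results.
4. Report observed n, SD, baseline-to-follow-up correlation and missing share by outcome, arm and visit. Base any later planning on observed values.
5. State what was filled, with which mean, and the denominator of the 40%. If only items were filled, give the rule and the count.

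In simulation, a REML model with Satterthwaite degrees of freedom held the error at 4.1-6.2% with two visits and 0-40% missing (2,500 runs per cell).

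The cost is SAP wording, one re-run and its disclosure, with somewhat wider intervals and some less favourable p-values. At ρ = 0.5, treating variances as known, the SE of the combined arm's change is √(0.75/k + 0.25/10 + 1/10 − 1/10) with k observed. That is 0.345 for k = 8 and 0.387 for k = 6, against the √(1/10) = 0.316 that arm-mean filling would report. No new data are needed.

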10.0 Study Design / Methods

ARMS 1, 2, and 3: Once a participant has consented and been enrolled they will be randomized by computer (stratified by gender) to one of three treatment groups and the PI and/or their designee will set up a home visit appointment to meet with the participant to obtain baseline data (Table 1). Part of the baseline screening includes the PROMIS Emotional Distress-Depression Short Form 8a. If a participant scores in the severe depression category (raw score 33 and above) a referral will be placed to a mental health professional. Additionally, participants that score in the moderate depression category (raw score 23 to 32) further screening for suicidal ideation will take place. If the participant would admit to suicidal ideation at any time during the study, an emergent mental health consult will be placed through the Charleston/Dorchester Mental Health Center Assessment/Mobile Crisis.

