restatement of the rationale (ie., that what one does affects how one feels and doing positive things will help one to feel positively), and problem solving. Behaviors that were consistently planned but not completed are removed and alternative behaviors suggested. The next 2 days' activities are planned. This session usually involves a significant amount of problem solving, and identification of avoidance, with planning in place to counter this avoidance. Sessions 3-4: These sessions begin with a review of homework, followed by asking the patient to state, in their own words, their interpretation of the rationale for Behavioral Activation. Obstacles to completing behaviors are discussed and additional exposure-based and reinforcing behaviors are generated. The next 2 day's activities are planned. Session 5: Includes discussion of the rationale and treatment gains obtained thus far. Discussion is also centered on the need to continue planning activities and using a daily planner for at least 6 months. Relapse prevention strategies are reviewed. Additional sessions are conducted every other week until week 12 (Otago and GYYB completion).

Table 2: Measurements/Instruments/Interventions and Time Points		
Major tasks and domains; monitor/ evaluate	Measures/instruments/questions and Cronbach's alpha ()	Data sources and time points
Screening	Ability to ambulate 150 feet with or without assistive device; Short version of Test for Functional Health Literacy in Adults (0.97) ³⁷ Tablet Computer Familiarity Questionnaire (0.92) ³⁸ Mini-Cog ²⁶	Participant interview and observation; Baseline
Demographics	Personal health, medical, health history—co-morbidities, medications, use of pain medications, race/ethnicity	Participant interview; Baseline
Weekly nursing self-management	Review weekly diary entries, pain scores, yoga and /or Otago progress, fatigue, and sleep.	Weekly
Reach: Sample Recruitment	Progress monitoring of sample representativeness; types of recruitment activities and rates; % eligible, consented, oriented	Tracking forms; weekly quality checks by PI; weekly team meetings
Effectiveness: Functional impacts Pain	Numerical rating scale NRS (0.99) ³⁹ PROMIS Pain Interference Short Form 6b (0.98) ⁴⁰ PROMIS Pain Behavior Short Form 7a (0.98) ⁴⁰ PROMIS Fatigue Short Form 6a (0.91) ⁴¹	Baseline; Daily; Study end Baseline; Study end Baseline; Study end Baseline; Daily; Study end

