The participant sample will be characterized using univariate descriptive statistics and frequency distributions for all variables as appropriate. We will also explore differences in demographic and other variables such as age (45-74, ≥ 75 years), sex, health status, functional activity, and QoL across the 2 time points.

Participant Compensation: Participants under ARMS 1, 2, and 3 will receive \$20 for screening, and \$20 at the initial enrollment visit for completion of the initial enrollment assessment and baseline surveys (total of \$40 if eligible and enrolled). Additionally, participants will receive another \$40 at successful completion of the post-treatment (week 12) and 3 month followup visits. Total compensation for successful study completion is \$120.00. All payments will be made to the participant in the form of a gift card.

Participants under the Supplemental ARM 4 will be provided a total amount of \$80 in study compensation \$40 for enrollment and completion of the baseline visit, and \$40 at successful completion of study at visit 2. Payment will be made in the form of a check that will be mailed to the participant's home address. Will collect social security numbers for MUSC IRS tax reporting purposes.

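### Aim 3's planning inputs come from mean-substituted data (which mean is not stated) and a three-arm ANOVA that names no contrast or interval, so a later RCT would probably be undersized

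*SAP*

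**What the plan says.** Protocol section 1.0 gives Aim 3 as: "Determine an initial efficacy signal for the intervention that will inform future power estimates". Its hypothesis is: "We hypothesize that the combined intervention will show significant within subject improvement over baseline on measures of pain, fatigue, and depression". The impact statement in the same section says the pilot "will set the stage for a full scale RCT demonstrating the additive benefit (if present) of each additional component" over Otago.

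Protocol section 3.0 says the trial "will use a 3x3 repeated measures (treatment x time) between groups randomized trial design", with assessments at baseline, post-treatment and 3 months. Section 10.0 has participants "randomized by computer (stratified by gender) to one of three treatment groups".

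The protocol's data analysis plan (section 12.0) covers feasibility proportions and means with 95% confidence intervals, descriptive statistics for all variables, and comparisons of eligible with ineligible people and of completers with non-adherers. It names no Aim 3 comparison.

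The SAP, written in the past tense, has one efficacy method: "Repeated measures analysis of variance (ANOVA) was used to determine significant differences for outcome variables between the 3 intervention Arms", at p<0.05. Missing values were filled by mean substitution. The SAP does not say whether the arm mean, the overall mean or some other mean was used, and its 40% limit on missing data is worded unclearly. Its confidence intervals are for proportions and mean responses, not for differences between arms.

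**The concern.** There are two linked problems, and the second is the more serious.

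First, the hypothesis, the test and the purpose do not line up. Improvement within the combined arm may reflect Otago alone, natural course or regression to the mean after entry on a pain-score threshold; none of these says what yoga or behavioral activation adds. The SAP turns to a between-arm test but does not say which term or contrast is to be reported. An omnibus p-value at 10 per arm is of little use for planning. What a later trial needs is the residual SD, the baseline-to-follow-up correlation and, with wide uncertainty, the two adjacent-arm differences.

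Second, mean substitution distorts those same quantities. Constants inserted at follow-up add apparent sample size without adding variation, and they carry no information about each person's own baseline. The SD and the correlation fall. Then either the interval becomes too narrow (arm mean) or the difference is pulled towards zero (overall mean).

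**Working it through.** **Inputs.** From the protocol: 3 arms of 10 (3 × 10 = 30, as stated), and Aim 2's hypothesis of less than 20% missing follow-up data. From the SAP: mean substitution and a 40% limit. The documents give no SD, effect size, power or correlation, so there is no power figure to reproduce. Assumed: one follow-up, unit SD, correlation rho of 0.5 (range 0.3 to 0.7), values missing completely at random, and 20% or 40% of follow-up values replaced. The 40% case is only one reading of the SAP's wording.

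**Step 1: closed-form check, arm mean, one arm.** With k of 10 values observed, the naive standard error is √((k−1)/9)/√10 and the correct one is 1/√k.
- k = 8: 0.279 against 0.354, ratio 0.79.
- k = 6: 0.236 against 0.408, ratio 0.58.

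**Step 2: closed-form check, overall mean.** If a fraction m in every arm is set to one common value, the expected difference becomes (1−m) times the truth: 0.8 × 0.5 = 0.40 SD, or 0.6 × 0.5 = 0.30 SD.

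**Step 3: simulation** (6,000 trials per setting, follow-up on arm and baseline, rho 0.5, adjacent difference 0.5 SD). The size ratio uses the SD alone with a fixed target difference, so required n is proportional to SD².

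| Replaced | Mean used | Residual SD, observed → substituted | 0.5 SD difference becomes | Coverage of nominal 95% interval | Size ratio |
|---|---|---|---|---|---|
| 20% | arm | 0.85 → 0.78 | 0.50 | about 88% | (0.78/0.85)² = 0.84 |
| 40% | arm | 0.85 → 0.68 | 0.51 | about 74% | (0.68/0.85)² = 0.64 |
| 20% | overall | 0.85 → 0.80 | 0.40 | – | (0.80/0.85)² = 0.89 |
| 40% | overall | 0.85 → 0.73 | 0.30 | – | (0.726/0.850)² = 0.73 |

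The correlation falls from about 0.49 to 0.43–0.44 (20%) or 0.36–0.38 (40%). Over rho 0.3 to 0.7 the size ratio runs from about 0.58 (arm mean, 40%, rho 0.3) to about 1.0 (overall mean, 20%, rho 0.7).

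**Step 4: effect on the arm-by-time test itself** (two time points, no true difference, rho 0.5 and 0.7, 2,000 to 3,000 replicates). After arm-mean substitution the 5% test rejects in about 8–10% of trials (20% replaced) or 15% (40%). After overall-mean substitution it stays near 5–6%.

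**Step 5: what observed data can give.** The 95% half-width of one adjacent, baseline-adjusted contrast is t × √(1−rho²) × √(2/n). With complete data (n = 10, 26 df, t = 2.056):
- rho 0.3: 2.056 × 0.954 × 0.447 = 0.88 SD
- rho 0.5: 2.056 × 0.866 × 0.447 = 0.80 SD
- rho 0.7: 2.056 × 0.714 × 0.447 = 0.66 SD

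Simulated at rho 0.5 with missing data, the half-width is about 0.92 SD (20%) or 1.1 SD (40%). After arm-mean substitution it appears to be 0.73 or 0.64 SD, so it narrows as data are lost.

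**The case against.** A repeated measures ANOVA contains a time factor, and its arm-by-time term uses baseline through change. A reader might infer that the SAP's model cannot address change at all; that is too strong. What remains is that the SAP states only a between-arm purpose and names no term, contrast or interval. A time effect pooled over arms is not the combined arm's change.

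Additive benefit is the later RCT's question, and Aim 3 speaks of the intervention as a whole. This is fair, and it is why the adjacent contrasts should be offered as imprecise pilot estimates rather than as an estimand the plan promised. It does not rescue the SD and correlation, which any later design needs.

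Baseline adjustment over change scores is partly a question of efficiency, and the gain is small when rho is high. That stands; the case does not depend on it.

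The 40% setting applies an unclear limit to follow-up values in every arm. That also stands, so the 40% figures are illustrative. The 20% figures show the same effect at a smaller size.

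Table 2 ("Table 2: Measurements/Instruments/Interventions and Time Points") lists the pain, fatigue and depression measures at baseline and study end, some also daily. A reader might infer that the analysis visit is undefined. Section 10.0 puts the exit interview after visit 2, and section 11.0 places the second visit at week 12, so study end most naturally means week 12. Only the content of the 3-month visit is open: section 10.0 pays participants "at successful completion of the post-treatment (week 12) and 3 month followup visits", and sections 3.0 and 11.0 also count a third visit.

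**Conclusion.** The point holds and should be acted on. Aim 3's hypothesis, the SAP's test and the planning purpose are not aligned, and the mean substitution, carried out as described, gives a wrong SD together with either intervals that are too narrow or a shrunken difference. Under the stated assumptions the consequence is mainly undersizing: a later trial at about 0.84 or 0.64 (arm mean) and 0.89 or 0.73 (overall mean) of the needed size at rho 0.5, and about 0.58 to 1.0 over rho 0.3 to 0.7. These figures rest on data missing completely at random and on assumed fractions; the documents do not give the actual fraction.

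Two stronger readings are not supported. A reader might infer that the direction of the error is unknown, because overall-mean substitution shrinks the difference and would inflate a sample size based on it. That requires sizing the RCT on the pilot difference, which 10 per arm is too imprecise to support; with a fixed target difference the SD governs. A reader might also count a significant within-arm change under equal improvement in all arms as a false positive of this plan. The SAP plans no such test, and the change would be real; the error would lie in crediting it to the added components.

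**What to change.** For each Aim 3 outcome (pain, fatigue, depression), replace mean substitution with an analysis of observed data: week-12 score on arm, own baseline and gender, with the missing-at-random assumption stated. Gender enters because randomisation was stratified by it; any gain in precision depends on its unknown relation to the outcome.

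Report:
- Otago + yoga minus Otago, and full package minus Otago + yoga, each with a 95% confidence interval and described as imprecise pilot estimates;
- the residual SD and the baseline-to-follow-up correlation, as the main planning inputs;
- within-arm changes as description only;
- which mean was substituted in the analysis already run, and what fraction of follow-up values it replaced.

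Reconcile the 3-month visit with Table 2 before adding any 3-month contrast. Mark the re-analysis as post hoc, since the SAP reports the analysis as done.

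The cost is a re-run on existing data, two residual degrees of freedom (27 to 25 with complete data), and wider intervals that show the actual uncertainty.
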